13.1. Adverse Events

Adverse events (AEs) will be coded using MedDRA Version 25.0, March 2022.

Treatment-emergent AEs, defined as those AEs occurring after the first administration of study treatment until end of study, will be tabulated in frequency tables by System Organ Class (SOC) and Preferred Term (PT) based on the Medical Dictionary for Regulatory Activities for each study period (Initial Period, Maintenance Period, and Follow-up Period). Missing date information will be handled using the algorithm described in Section 8.3.

Additional summary tables by SOC and PT will be provided for SAEs, AEs related to the study drug(s), AEs related to the study procedure, adverse events of special interest (AESIs), and AEs leading to treatment discontinuation and study withdrawal.

AEs will be summarized using the number and percent of subjects reporting each SOC and PT and sorted alphabetically by SOC and by descending frequency of PT within SOC.

Subjects who experienced multiple events within the same SOC will be counted once in the SOC summary. When summarizing by causality or maximum severity, if a subject experiences more than 1 occurrence of the same AE, the occurrence with the greatest severity and the closest association with the study drug will be used in summary tables. For summary by maximum severity, subjects who experience multiple occurrence of an AE, the most severe category for each SOC and for each PT within each SOC will be considered in the summary.

TEAEs related to study drug/study procedure are those that are identified as reasonable possibility.

If relationship or severity is missing, the event will be considered as AE related to study drug/study procedure or severe AE.

An AESI is a noteworthy treatment-emergent event for the study drug that should be monitored closely and reported promptly. An AESI can be either serious or non-serious. Based on the potential risks of nemolizumab and the risks associated with biologics in general (i.e., class effects), the following AEs will be considered as AESIs: Injection-related reactions, Newly diagnosed asthma or worsening of asthma, Infections, Peripheral edema:limbs, bilateral, Facial edema and elevated ALT or AST (>3xULN) in combination with elevated Bilirubin (>2xULN).

The following summary tables for TEAEs will be presented for all TEAEs (i.e., TEAE, all causalities) and study drug related TEAEs separately and by period (treatment period which includes Initial Period and Maintenance Period) and Follow-up Period.

- Overall Summary of TEAEs
Overall summary table includes summary of subjects reporting TEAEs, TEAE related to study drug, TEAE related to protocol procedure (including topical background therapy), Serious TEAE, Serious TEAE related to study drug, Severe TEAE, TEAE leading to temporary discontinuation of

This document is confidential.

study drug, TEAE leading to permanent discontinuation of study drug, TEAE leading to permanent discontinuation from study, TEAE of special interest, TEAE leading to death, TEAE related to study drug leading to death. For the summary of Follow-up period, the summaries of 'temporary discontinuation of drug' and 'permanent discontinuation of drug' will not be provided.

- TEAEs by System Organ Class and Preferred Term
- Serious TEAEs by System Organ Class and Preferred Term
- TEAEs by System Organ Class, Preferred Term and Maximum Severity
- Severe TEAEs by System Organ Class and Preferred Term
- TEAEs Leading to Permanent Discontinuation of Study Drug by System Organ Class and Preferred Term, which is only for Treatment period. No summary of Follow-up period.
- TEAEs occurred in \geq 5% of subjects by System Organ Class and Preferred Term
- TEAEs occurred in \geq 5% of subjects by Preferred Term

For overall study period which includes all periods (initial, maintenance and follow-up), the following summary tables will also be presented and repeated for all TEAEs (all causalities) and study drug related TEAEs.

- Overall Summary of TEAEs
- TEAEs by System Organ Class and Preferred Term

The overall study period summary will be presented by 4 treatment groups (Nemolizumab 30mg Q4W, Nemolizumab 30mg Q4W to Q8W, Nemolizumab 30mg Q4W to Placebo, and Placebo). Nemolizumab 30mg Q4W includes all subjects in the population who received Nemolizumab 30mg in Initial Period or who received Nemolizumab 30mg Q4W continuously during Initial and Maintenance Periods. Similarly, Placebo includes all subjects in the population who received Placebo in Initial Period or who received Placebo continuously during Initial and Maintenance Periods.

For the subset of subjects with COVID-19 infection, the following summary tables will be provided additionally and it will be repeated for all TEAEs and Study drug related TEAEs, separately.

- Overall summary of TEAEs
- TEAEs by System Organ Class and Preferred Term
- Serious TEAEs by System Organ Class and Preferred Term
- TEAEs of Special Interest by Category, System Organ Class and Preferred Term

A separate summary below for TEAEs of Special Interest will be provided by periods (initial, maintenance) and repeated for all TEAEs (all causalities) and Study drug related TEAEs.

- Overall Summary of TEAEs of Special Interest
- TEAEs of Special Interest by Category, System Organ Class and Preferred Term
- TEAEs of Special Interest by Category, System Organ Class, Preferred Term and Maximum Severity

Adjudicated events will also be summarized as below by periods (initial, maintenance) and repeated for all TEAEs (all causalities) and Study drug related TEAEs.

This document is confidential.

- Adjudicated TEAEs by System Organ Class and Preferred Term, which are confirmed by Independent Adjudication Committee (IAC).
- Confirmed Adjudicated TEAEs by System Organ Class, Preferred Term and Maximum Severity. Maximum severity will be based on the severity adjudicated by IAC.
- Asthma TEAEs and TEAE of Special Interest reported by Investigator with Adjudication by IAC, which include the data reported by Investigator and adjudications by IAC.

The subgroup summary by country and age group will also be provided for the following summaries. It will be repeated for all TEAEs and Study drug related TEAEs and for Treatment period, Follow-up period and Overall period, separately.

- Overall summary of TEAEs
- TEAEs by System Organ Class and Preferred Term

In addition, the exposure-adjusted incidence rate (i.e., number of subjects per 100 patient-years) will be summarized for all TEAEs (all causalities) and study drug related TEAEs during Treatment Period.

Exposure-adjusted incidence rates of TEAEs is defined as the number of subjects exposed to treatment and experiencing a certain event divided by the total time of all subjects who are at risk for the event. Specially, for subjects with no event the exposure time is the time from the first drug intake to the end of treatment period. Exposure years is calculated as last study drug exposure date minus first study drug exposure date plus one, divided by 365.25 which is the number of days count in a year. This exposure year calculated for each subject is then added cumulatively and is derived for each treatment arm. So each treatment arm will have one value for exposure years (aka. patient years). The exposure year calculation is different in case of subjects who have completed the study or discontinued from the study or having withdrawn from the study due to any reason. Only the event occurred during the treatment period will account for calculation.

Subject listings will be presented for all TEAEs, TEAEs of special interest, serious TEAEs, severe TEAEs, TEAE leading to permanent discontinuation of study drug, TEAEs leading to death and pre-treatment AEs. Subject listings of TEAEs for subjects with COVID-19 infection and adjudicated Asthma TEAEs will also be listed.

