### 9.2.1 Adverse Events

#### Adverse Event Definition

An AE is defined as any untoward medical occurrence in a clinical study subject administered a medicinal product which does not necessarily have a causal relationship with this treatment. An AE can therefore be any unfavorable and unintended sign (including an abnormal laboratory finding), symptom, or disease temporally associated with the use of a medicinal (investigational) product, whether or not it is related to the medicinal (investigational) product. This includes an exacerbation of pre-existing conditions or events, intercurrent illnesses, drug interaction, or the significant worsening of the indication under investigation that is not recorded elsewhere in the CRF under specific efficacy assessments.

Note(s):

- Any new sign or symptom reported by the subject that appears after accidental or intentional overdose or misuse should be reported as an AE.
- Whenever possible, a diagnosis should be reported on the AE form, instead of signs, symptoms, or abnormal laboratory values.
- Pregnancy is not to be considered an AE; however, it must be monitored and reported as described in Section 9.2.1.5.
- Each worsening of a chronic disease from the screening visit should be reported as a new AE.

The investigator or designee will report all AEs that occur from the time the ICF is signed until the end of the study. The sponsor/CRO should be informed if the investigator becomes aware of any safety information that appears to be drug related, even after the subject has completed the clinical study.

At each post-enrollment visit, the investigator (or sub-investigator) will question the subject about AEs using an open non-persuasive question to elicit reporting of AEs (for example, "Have you noticed any change in your health since the last visit?"). Directed questioning and examination will then be performed as appropriate.

CONFIDENTIAL

Any AE occurring during the AE reporting period, whether it is related to the study drug(s) or not, will be recorded immediately in the source document and described on the Adverse Event Form (“AE Form”) along with the date of onset, severity, relationship to the study drug(s), and outcome, without omitting any requested and known information. Additional information will be requested under certain circumstances.

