### **Assessment of Severity**

Each AE will be assigned a category by the investigator as follows:

- Mild: An AE that is easily tolerated by the subject, causes minimal discomfort, and does not interfere with everyday activities.
- Moderate: An AE that is sufficiently discomforting to interfere with normal everyday activities; intervention may be needed.
- Severe: An AE that prevents normal everyday activities; treatment or other intervention usually needed.

If there is a change in severity of an AE, it must be recorded as a separate event.

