#### **10.1.4.2 Adverse Events**

Treatment-emergent AEs, defined as those AEs occurring after the first administration of study treatment until the last study visit, will be tabulated in frequency tables by system organ class and preferred term based on the Medical Dictionary for Regulatory Activities for each study phase. Additional summary tables will be provided for SAEs, AEs related to the study drug(s) (reasonable possibility, no reasonable possibility), AEs related to the study procedure, AESIs, and AEs leading to treatment discontinuation and study withdrawal. For a given AE, a subject will be counted once even if he/she has experienced multiple episodes of that particular AE.

Pretreatment AEs will be listed separately.

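### Read literally, the timing-only definition of a treatment-emergent AE counts an event that began before first dose and merely eased afterwards, and may count an easing event again in the next period

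*SAP*

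**What the plan says.** Recording. Under Assessment of Severity in protocol 9.2.1, the rule is: "If there is a change in severity of an AE, it must be recorded as a separate event". It names no direction, so a step down opens a record just as a step up does. Collection starts before dosing: "The investigator or designee will report all AEs that occur from the time the ICF is signed until the end of the study".

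Classification. SAP 13.1 gives "Treatment-emergent AEs, defined as those AEs occurring after the first administration of study treatment until end of study". Protocol 10.1.4.2 likewise has TEAEs "defined as those AEs occurring after the first administration of study treatment until the last study visit", and adds: "Pretreatment AEs will be listed separately". SAP 8.3 settles emergence from dates, imputing missing start dates for that purpose. Neither document compares a post-dose record with the severity before it.

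Tabulation. SAP 13 and 13.1 call for summaries of the initial, maintenance and follow-up periods. AESI and adjudicated asthma events are summarised by initial and maintenance period, and there are also tables for the overall study. Protocol 10.1.4.2 states: "For a given AE, a subject will be counted once even if he/she has experienced multiple episodes of that particular AE". SAP 13.1 counts a subject once per system organ class and takes the worst occurrence when summarising severity. No rule says how an AE record is placed in a period. SAP 9.4 and 9.5 do give such rules for procedures and medications.

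**The concern.** The recording rule and the definition are each workable alone. Together they let an improvement create a treatment-emergent event. A moderate screening-period AE that falls to mild after Day 1 generates a second record. If that record starts on the date of the change, it meets the definition. Had the AE stayed moderate, it would have appeared only in the pre-treatment listing.

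The same mechanism can act at Week 16 and at the end of treatment. There the stake is attribution: an event that began on nemolizumab Q4W could appear in the maintenance table under Q8W or placebo because it got better.

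The missing condition is used elsewhere in the protocol. Section 9.2.2 reports an out-of-range laboratory value as an AE only if it was absent at screening or has worsened since. Section 9.2.1 treats each worsening of a chronic disease as a new AE.

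**Working it through.** The documents give no figure to reproduce. The check applies the written rules to six illustrative AE histories, then repeats them with a condition that a record must be new or worse than the one before it.

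Rules applied:
- Each severity change opens a record (protocol 9.2.1).
- A record is a TEAE if it starts on or after Day 1 (SAP 13.1, protocol 10.1.4.2).
- A subject counts once per preferred term per period (protocol 10.1.4.2).

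Assumptions, because the documents are silent:
- The new record starts on the date of the severity change.
- A record belongs to the period in which it starts: Initial is Days 1 to 112, Maintenance is Days 113 to 336, and Follow-up comes after. This fits the target days of 113 for Week 16 and 337 for Week 48 in SAP 8.4.

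| AE history | Literal rules: TEAE records; subject counts | New-or-worsened: TEAE records; subject counts |
|---|---|---|
| A. Severe before dosing, mild on Day 20 | 1; Initial 1 | 0; none |
| B. Moderate on Day 30, mild on Day 50 | 2; Initial 1 | 1; Initial 1 |
| C. Moderate on Day 100, mild on Day 120 | 2; Initial 1 and Maintenance 1 | 1; Initial 1 |
| D. Moderate on Day 100, unchanged into Maintenance | 1; Initial 1 | 1; Initial 1 |
| E. Moderate before dosing, unchanged | 0; none | 0; none |
| F. Moderate on Day 330, mild on Day 340 | 2; Maintenance 1 and Follow-up 1 | 1; Maintenance 1 |

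Reading across:
- **A against E.** The improving event is a TEAE and the unchanged one is not. This does not depend on the period rule. A also enters the overall-study table and the numerator of the exposure-adjusted rate.
- **C against D.** The improving event is counted in two periods and the unchanged one in a single period. F repeats this at the end of treatment. These results do depend on assignment by record start date. If the medication rule in SAP 9.5 (started, stopped or ongoing) were carried over to AEs, D would also count in Maintenance, so the severity change would no longer make the difference. If records were assigned by original onset, C would count in Initial only.
- **B.** Within one period the subject count stays at 1. Only the listing gains a record.
- **Overall-study tables.** C and F each count one subject once.

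**The case against.** The strongest reply is that the start date is inferred. Protocol 9.2.1 asks for the date of onset and the date of first occurrence. A separate record that kept the original date would neither become a TEAE nor move period. The CRF completion rules that would settle this are not in the documents. This stands as an assumption to state. The plain sense of a separate event is that it has its own dates, and the analysis text does nothing to secure the other reading.

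A second reply is that SAP 13.1 can be read as combining initial and maintenance into one treatment period for the main TEAE tables. That would remove case C from those tables. It would leave case A, case F, and the AESI and adjudicated asthma tables, which are split by initial and maintenance period.

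Several stronger readings are tempting and are not supported:
- **TEAE incidence is inflated generally.** Subject-once counting and the maximum-severity rule neutralise a step down within a period.
- **Event counts are inflated.** The visible tables count subjects, and the exposure-adjusted rate is subjects per 100 patient-years. Extra records show only in listings.
- **The comparison of maintenance regimens is biased.** The three re-randomised arms are drawn 1:1:1 from the same responders. AEs ongoing at Week 16 are therefore balanced in expectation, as is the carry-over unless improvement differs by arm. The documents give no evidence that it does, and SAP section 13 plans no between-arm safety tests.

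**Conclusion.** The point holds in a limited form. As written, a pre-dose AE that only improves after Day 1 is classed as treatment-emergent, given that the new record carries the date of the change. Under the further assumption of assignment by record start date, an AE that eases after Week 16 or after end of treatment is counted again in the next period's table, under the re-randomised arm where that applies. Only events that span a boundary are affected.

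The size cannot be computed. A reader might estimate it by guessing the share of subjects with an AE ongoing at a boundary and the share of those who step down, but the documents supply neither. They do give the scale of one miscounted subject. Protocol 8.1 expects about 190 nemolizumab responders, so 190 / 3 = about 63 per arm, and 1 / 63 = 1.6 percentage points. That is not an estimate of how many would be miscounted.

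Efficacy inference is untouched. The correction is worth making because a stated rule gives a wrong classification and the remedy is cheap.

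**What to change.** In SAP 13.1:
- Define a TEAE as an AE with onset after first dose, or one present before first dose that worsens in severity afterwards.
- Link severity-change records to their parent event using the recorded AE data. State the linking rule: matching only on preferred term and adjoining dates could merge distinct events.
- Assign the event to the period of parent onset. Count it in a later period only if it worsens there, at the severity reached in that period. Reporting the maximum severity in the period of onset would be wrong, because it would charge a later worsening to the earlier treatment.

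Protocol 10.1.4.2 carries the same timing-only definition, so the change is a departure from the protocol and belongs in SAP section 15, which at present lists only the concomitant-therapy definition.

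Cost: one derivation in the AE dataset and one entry in SAP section 15. Sites go on recording as they do now.

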#### **Subjects who receive rescue therapy will be considered non-responders.**

Based on the phase 2b results (Protocol 114322), it is estimated that 15% of subjects will drop out from the initial treatment period. Assuming a 45% responder rate in active treatment and 12% with placebo, approximately 216 subjects will participate in the maintenance period (190 nemolizumab and 26 placebo subjects).

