4.1. Brief Description

This is a randomized, double-blind, placebo-controlled, multicenter, parallel-group study in adult and adolescent subjects with moderate-to-severe AD. Eligible subjects must have a documented history of inadequate response to topical AD medication(s).

Approximately 750 total subjects will be randomized (2:1) to receive either nemolizumab (CD14152) or placebo, stratified by Baseline disease severity (Investigator's Global Assessment [IGA]; moderate: IGA = 3; severe: IGA = 4) and peak pruritus numeric rating scale (PP NRS) severity (PP NRS \geq 7; PP NRS < 7). A minimum of 250 subjects will be randomized in each PP NRS strata. Clinical responders at Week 16 who were treated by Nemolizumab during Initial Period (i.e., the end of Initial treatment/beginning of Maintenance) will be re-randomized (1:1:1) to different treatment regimens (injections every 4 weeks [Q4W] or every 8 weeks [Q8W] of nemolizumab [CD14152] or placebo Q4W). All placebo-treated subjects (i.e., subjects in placebo from the Initial Period) who responded to placebo during the Initial Period will continue to receive placebo Q4W in the Maintenance Period.

The study consists of 4 Periods over approximately 60 weeks: Screening (including run-in), Initial, Maintenance, and Follow-up (unless the subject is a non-responder at Week 16, at which their participation could last up to 28 weeks).

Screening Period:

The Screening Period (approximately 2-4 weeks before planned Day 1/Baseline) will evaluate subject eligibility and introduce standardized background topical therapy over a Run-in Period of at least 2 weeks (i.e., 14 days) before Day 1/Baseline. Subjects may be rescreened once unless the reason for screen failure is related to disease severity inclusion criteria (IGA, EASI, BSA, and PP NRS). The latter subjects are not permitted to rescreen.

Initial Period:

The Initial Period is defined as Day 1/Baseline through Week 16 (before the Week 16 dose, with last dose at Week 12). Eligible subjects will be randomized in a ratio of 2:1 at Baseline to receive subcutaneous injections of nemolizumab (CD14152) (i.e., group 1) or placebo Q4W (i.e., group 2).

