Clinical assessments will occur according to the schedule of assessments through the Week 16. Subjects who are clinical responders at Week 16 will continue to the Maintenance Period. Subjects who discontinue the Initial Period prematurely should complete an Early termination (ET) visit and a Follow-up visit 12 weeks after the last study drug injection. Subjects who are non-responders at Week 16 may be eligible to enroll into the LTE study (Protocol 118163). Subjects who require rescue therapy for clinical worsening of AD before Week 16 may also be considered for LTE study participation but will be required to continue with study visits until the Week 16 visit is due. The Follow-up visit is not required for subjects who participate in the LTE study.

Maintenance Period (Re-Randomization: Week 16 to Week 48):

The Maintenance Period is defined as Week 16 (Maintenance Baseline) to Week 48. All nemolizumab (CD14152)-treated subjects (i.e., group 1) who are clinical responders at Week 16 will be re-randomized (1:1:1) to study medication, as follows: group 1A, nemolizumab (CD14152) 30 mg Q4W; group 1B, nemolizumab (CD14152) 30 mg Q8W; or group 1C, placebo Q4W.

This document is confidential.

[figure not shown]
All placebo-treated subjects (i.e., subjects in group 2 from the Initial Period) who responded to placebo during the Initial Period will continue to receive placebo Q4W in the Maintenance Period. Beginning at Week 16, subjects in group 1A will receive active (i.e., nemolizumab [CD14152]) study drug injections Q4W up to Week 44. Subjects in group 1B will receive active (i.e., nemolizumab [CD14152]) study drug injections Q8W, with placebo at alternating visits to maintain the blind. Group 1B subjects will receive the last active study drug injection at Week 40 (final injection at Week 44 will be placebo). Group 1C subjects will receive placebo Q4W (i.e., through Week 44).

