6.3. Safety Population

The safety population will comprise all subjects in ITT population who receive at least 1 dose of study drug. All safety data will be summarized based on the safety population under the treatment group 'as treated'.

For Maintenance Period, only subjects in ITT population who received at least one drug in the Maintenance Period will be included in the population.

Subject who are treated on error during the course of the study will be assigned to actual treatment as described below.

Initial Period:

- Subjects who are randomized to Placebo but treated at least once with Nemolizumab in error will be assigned to 'Nemolizumab Q4W'.
- Subjects who are randomized to Nemolizumab but treated at least once with Placebo in error will still be assigned to 'Nemolizumab Q4W'. If they always received Placebo in error during the period, then they will be assigned to 'Placebo'.

Maintenance Period:

- Subjects who are re-randomized to Nemolizumab Q4W but treated at least once with Placebo in error will be assigned to 'Nemolizumab Q4W to Q4W'.
- In case of subjects who re-randomized to Nemolizumab Q8W, they are supposed to receive Nemolizumab and Placebo alternately. If they are treated with Nemolizumab instead of Placebo at least once in error, they will be assigned to 'Nemolizumab Q4W to Q4W'. However if they are treated at least once with Placebo instead of Nemolizumab in error will be assigned to 'Nemolizumab Q4W to Q8W'.

This document is confidential.

- Subjects who are re-randomized to Placebo but treated with Nemolizumab at least once in error will be assigned to 'Nemolizumab Q4W to Q4W'.
- Subjects who are randomized to Placebo for Initial Period and continue the Maintenance Period will be assigned to 'Placebo' even if treated with Nemolizumab at least once in error.

Overall Period:

- If subjects exited the study after Initial Period (i.e., not re-randomized nor continued with Placebo for Maintenance Period), overall period treatment group will be the same with Initial period treatment group assigned (i.e., can be either 'Nemolizumab Q4W' or 'Placebo').
- In case subjects who re-randomized for Maintenance Period,
 - Subjects who are re-randomized to Nemolizumab Q4W will be assigned to 'Nemolizumab Q4W' even if they treated by Placebo in error during the study.

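### Overall-study-period TEAE tables: the nemolizumab arm is split by Week 16 outcome and shown as n (%) only, so columns with very different follow-up are set side by side

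*SAP*

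**What the plan says.** SAP 13.1 defines an overall study period that spans the initial, maintenance and follow-up periods. For it the SAP plans two kinds of TEAE table: the overall summary and TEAEs by system organ class and preferred term. Each is given for all causalities and for drug-related events, and is repeated by country and by age group. On the columns: "The overall study period summary will be presented by 4 treatment groups".

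SAP 6.3 says who goes where. For subjects who exit after the Initial Period, the "overall period treatment group will be the same with Initial period treatment group assigned". Subjects re-randomised to Q4W stay in the Q4W column. Those re-randomised to Q8W or placebo get columns of their own. Placebo subjects who continue into maintenance stay under placebo. Only nemolizumab subjects "who are clinical responders at Week 16 will be re-randomized (1:1:1) to study medication", so in that arm alone the column depends on the Week 16 outcome.

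Adverse events are tabulated as number and percent of subjects. Exposure-adjusted incidence rates "will be summarized for all TEAEs (all causalities) and study drug related TEAEs during Treatment Period". The index of tables agrees: Tables 14.3.1.4.1 and 14.3.1.5.1 are Treatment Period tables, and none is listed for the overall study period.

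The two sections do not quite match. SAP 13.1 describes the Q4W column as taking in every subject who had nemolizumab 30 mg in the Initial Period, or who had Q4W throughout. Taken literally, that is all 500.

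**The concern.** A column defined by what happened at Week 16 is not a randomised group. The Q4W column keeps every nemolizumab subject who stopped, dropped out or did not respond, plus one third of the responders. The two switch columns contain only subjects who reached Week 16 on study as responders and were then planned for 32 more weeks. The placebo arm is never split.

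A crude percentage rises with time at risk. Even if the drug had no effect on adverse events, these tables would therefore show a clear excess in the Q8W column and in the column withdrawn to placebo. Maintenance safety is part of the secondary objective, and the overall summary carries rows for serious events, events of special interest and events leading to discontinuation. A reader going to the whole-study table for those rows could draw the wrong conclusion. The wording mismatch adds a practical risk: two programmers could produce Q4W denominators of about 373 and 500 from the same SAP.

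**Working it through.** **Inputs**
- Randomised: "Approximately 750 total subjects will be randomized (2:1) to receive either nemolizumab (CD14152) or placebo" (SAP 4.1), so 500 and 250.
- Dropout, from the maintenance paragraph of the Protocol Synopsis: "it is estimated that 15% of subjects will drop out from the initial treatment period".
- Week 16 response rates, from the same paragraph: "Assuming a 45% responder rate in active treatment and 12% with placebo".
- Planned time from Day 1 (Protocol 8.5, less the 4-week screening): Week 16 exits 16 weeks, or 24 with the follow-up visit; responders 48, or 56.

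**The protocol's own figure.** 500 × 0.85 × 0.45 = 191.25 and 250 × 0.85 × 0.12 = 25.5, total 216.75. The protocol has "approximately 216 subjects will participate in the maintenance period (190 nemolizumab and 26 placebo subjects"), so it reproduces to rounding. I use 190 and 26 below.

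**Column sizes under SAP 6.3**
- Each re-randomised arm: 190/3 = 63.3.
- Q4W column: (500 − 190) + 63.3 = 373.3. Responder share 63.3/373.3 = 17%, against 190/500 = 38% in the arm as randomised.
- Placebo column: 250, with 26/250 = 10.4% responders.

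**Mean planned time**

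| Column | To end of treatment | With follow-up visit attended by all |
|---|---|---|
| Q4W | (310 × 16 + 63.3 × 48)/373.3 = 21.4 weeks | 29.4 |
| Placebo | (224 × 16 + 26 × 48)/250 = 19.3 | 27.3 |
| Q4W to Q8W; Q4W to placebo | 48 | 56 |
| Ratio, switch to Q4W | 48/21.4 = 2.24 | 56/29.4 = 1.90 |

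**Crude percentages with no true difference.** Assume one constant hazard in every column and no dropout within periods. Let p be the assumed 16-week risk; the documents give none. The 48-week risk is P = 1 − (1 − p)³. The Q4W column shows (310p + 63.3P)/373.3, placebo shows (224p + 26P)/250, and each switch column shows P.

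| p | Q4W | Placebo | Switch columns | Switch/Q4W |
|---|---|---|---|---|
| 5% | 6.6% | 6.0% | 14.3% | 2.17 |
| 10% | 12.9% | 11.8% | 27.1% | 2.10 |
| 20% | 24.9% | 23.0% | 48.8% | 1.96 |
| 30% | 36.1% | 33.7% | 65.7% | 1.82 |
| 40% | 46.5% | 44.0% | 78.4% | 1.69 |

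These count time to end of treatment. If everyone attended follow-up, the exponents become 24/16 = 1.5 and 56/16 = 3.5, and the ratio runs from 1.84 (p = 5%: 16.4%/8.9%) to 1.42 (p = 40%: 83.3%/58.6%).

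**Initial-period events followed by exit.** All such subjects stay in the Q4W numerator, while the denominator falls from 500 to 373.3. The inflation is 500/373.3 = 1.34. A true 5% is 25 subjects, shown as 25/373.3 = 6.7%. The placebo figure is unchanged.

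**Would pooling the arm cure it?** Crude all-nemolizumab against all-placebo at p = 30% gives (310 × 0.30 + 190 × 0.657)/500 = 43.6% against 33.7%. The gap with no true difference grows from about 2 to about 10 points, because mean planned time is then (310 × 16 + 190 × 48)/500 = 28.2 weeks against 19.3.

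**The case against.** The strongest reply is that the sound comparisons are already planned. SAP 13 promises every safety endpoint by Initial, Maintenance and Follow-up Period. SAP 13.1 repeats this for TEAEs, and plans special-interest and adjudicated events by period for initial and maintenance. The Initial Period summaries keep 500 against 250 over 16 planned weeks each, and the maintenance summaries address maintenance safety directly. Serious, severe and discontinuation tables by preferred term are not planned for the overall period. No safety hypothesis test is specified, and SAP 9.6 summarises exposure for initial and maintenance combined, so unequal treatment duration would be visible. All of this stands, and it limits the importance of the point.

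Four stronger readings are tempting, and the documents do not support them:
- *That Q4W against placebo is badly distorted.* For any TEAE the gap with no true difference is 0.6 to 2.5 points across the table above. The two columns have similar mean time (21.4 and 19.3 weeks), and the Q4W column still has a larger share of responders than placebo (17% against 10.4%). The exception is events that lead to exit.
- *That the safety plan uses crude percentages throughout.* Exposure-adjusted rates are planned for the Treatment Period, which SAP 13.1 describes as including initial and maintenance. They are missing only from the overall-period tables.
- *That Q4W-phase events are misattributed in the Q4W-to-placebo column.* That column names a sequence, and such events belong in it. The difficulty is unequal time.
- *That the switch columns are always followed more than twice as long.* The mean ratio is 2.24 to end of treatment, but about 1.9 if all attend follow-up.

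The 373 and 1.34 also depend on exclusive columns. SAP 6.3 points that way, although its rules for re-randomised subjects are written around dosing errors. The literal wording of SAP 13.1 would put all 500 in the Q4W column and make the columns overlap. That is a reason to settle the text.

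**Conclusion.** The point holds for the overall-study-period TEAE tables and their causality, country and age repeats. They sort one arm by a post-randomisation outcome, leave the other whole, and show n (%) over unequal follow-up. With equal hazards the switch columns would look roughly twice as high as Q4W: 1.7 to 2.2 times on treatment time, less if follow-up is fully attended. Events that lead to exit by Week 16 would be inflated about 1.34-fold in the Q4W column.

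The sizes rest on the protocol's planning figures, on exclusive columns, and on my assumptions of a constant hazard and no dropout within periods. Early exits from the switch columns, such as rescued subjects moving to the extension study, would reduce the gap. Higher response would too: applying the 49% and 19% EASI-75 rates to all randomised subjects, the Q4W column is about 337 and the treatment-time ratio 2.02.

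This is a cheap improvement to a descriptive table set. It does not undermine the main safety comparison.

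**What to change.** In SAP 6.3 and 13.1, for the overall-period tables:
1. Assign events and time at risk by regimen at event onset. All initial-period nemolizumab events and time go under Q4W; later events and time go under the re-randomised arm. Placebo is unchanged.
2. Report exposure-adjusted rates per 100 patient-years beside n (%).
3. If the four sequence columns are kept, still add the rates. Footnote that the columns are defined after randomisation and have unequal follow-up, and make the SAP 13.1 description of the Q4W column agree with SAP 6.3, stating plainly that each subject appears in one column.
4. Do not show crude all-nemolizumab (500) against all-placebo (250) percentages for the overall period without exposure-adjusted rates, since that widens the gap that arises with no true difference.

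The cost is SAP wording and some reprogramming of these tables; no new data are needed. Under item 1 some subjects contribute to more than one column, which needs a footnote.
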